#### 3.4 Secondary outcomes

- 1. Relapse requiring NIV (defined as recurrent AHRF>48 hours after removal of ventilator).
- 2. Total duration of ventilation.
- 3. Length of hospital stay.
- 4. NIV complications (incidence and severity).
- 5. Patient reported outcome measures: Modified Borg dyspnoea scale\*; Sputum clearance via visual analogue scale\*; Richards-Campbell sleep questionnaire\*; Hospital Anxiety and Depression Scale (HADS) pre-discharge; St Georges Respiratory Questionnaire for COPD (SGRQ-C) and EQ-5D-5L days 7, 30 and 90 post-randomisations.
- 6. Mortality in-hospital and 90-days post-randomisation.
- 7. Readmissions 30-days post-discharge.
- 8. Health economic analysis:
  - Costs to the NHS in terms of provision of the interventions (both on a respiratory support unit and a critical care unit) and cost implications of subsequent resource utilisation up to 90 days follow up;
  - Cost utility analysis using EQ-5D-5L quality adjusted life years (QALYs).
- 9. Responder analysis within the accelerated weaning group to identify predictors of success/failure.
- \*Day 1 to 5.

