## 7.7 Trial Assessments

The following assessments will be completed during the acute phase of the trial.

Following confirmation of inclusion/exclusion criteria and informed consent, patients will undergo baseline assessment and randomisation. Baseline assessment will include sociodemographic details, full medical history, COPD history (confirmation of diagnosis and severity), details of index admission and NIV management.

On days 1 to 5, patients will be asked to complete the following assessments:

- 1) score their level of breathlessness on the Modified Borg breathless scale (score 0 not breathless at all to 10 maximal breathlessness);
- 2) their ease of sputum clearance on a visual analogue scale (score 0 very easy to 10 very difficult); and
- 3) their level of sleep quality via the Richards-Campbell questionnaire.

NIV status and weaning data will be recorded daily during admission.

Healthcare resource utilisation costs and mortality will be monitored during the in-hospital stay.

Spirometry will be performed pre-discharge if no previous spirometry confirming airflow obstruction is available.

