#### 7.8 Long-term Follow-up Assessments

The following assessments will be completed at set timepoints during the follow up phase of the trial.

- 7 days post-randomisation (within 10 days of the scheduled assessment): Hospital Anxiety and Depression Scale (HADS); St George's Respiratory Questionnaire for COPD (SGRQ-C); and EQ-5D-5L.
- 30 days post randomisation: Healthcare resource utilisation costs; SGRQ-C; EQ-5D-5L (within 10 days of the scheduled assessment); spirometry (30 days since last intercurrent exacerbation).
- 30 days post discharge: Readmissions.

ISRCTN: 64639614 IRAS: 313485 CPMS: 53277

- 90 days post randomisation: Healthcare resource utilisation costs; Mortality.
- 90 days post randomisation (within 14 days of the scheduled assessments): SGRQ-C and EQ-5D-5L

Informed consent will be reconfirmed at each assessment with participants pre-discharge from hospital, and at 30 and 90-days post-randomisation.

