#### 10.3.3 Secondary outcome analysis

For all outcomes (both primary and secondary) we will present the characteristics, including those stratified by the weaning strategies. We will describe all baseline characteristics, follow-up measurements using suitable measures of tendencies: means and median with the associated standard deviation, 95% confidence interval and interquartile ranges for continuous variables and frequency and proportions for categorical variables (including binary variables). We will use Chi-Square test (or Fisher's Exact test in case of small number of observations) if the variable is categorical and will use t-test if the variable is continuous. For variables that are not parametric we will use Mann-Whitney U test. We will use the critical alpha 5% (thus p-value < 0.05 will be considered statistically significant) and we will also present the 95% confidence interval. Analyses will be performed by intention to treat, with secondary analyses of primary and secondary outcome based on protocol adherence. All analyses will be done in  $R^{15}$  and SPSS.  $R^{16}$ 

All baseline patient characteristics and outcomes will be included in the imputation mode. Mean change in quality of life over 90 days (SGRQ-C, EQ5D5L) from baseline will be calculated. In-hospital and 90-day mortality, and readmission within 30-days: time from discharge to death and time to readmission will be analysed using a Cox proportional hazards regression model, adjusted for covariates. For this analysis, no interaction between interventions will be assumed. Analysis will be two-sided at 5% level. We will also report the model performance by C-statistic. A sensitivity analysis will be performed with the log-rank test stratified by the centre. As we are only capturing readmission within 30 days, we will compare the proportion adjusted for the covariates (In-hospital mortality=NIVO; Readmission=PEARL: previous admission, extended MRC Dyspnoea scale, age, left and right heart failure).

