#### 10.9 Economic evaluation

An embedded economic evaluation will estimate the cost effectiveness (CE) and cost utility (CU) of the accelerated weaning protocol in comparison with standard care for NIV weaning from an NHS perspective. Costs of the protocols, resource use and associated costs will be estimated during the index admission for ECOPD up until discharge from electronic hospital records, and will include critical care, respiratory support unit and general ward length of stay (LOS). In addition, NHS resource use (primary, secondary and community care) and associated costs will be captured up until 90 days post-randomisation, triangulated from a number of sources. At discharge, participants will be given a heath resource diary to record events related to any COPD and non-COPD associated treatment they receive during the study. The diary is divided into four sections: (i) GP resources; (ii) hospital outpatient resources; (iii) accident and emergency (A&E) resources; and (iv) hospital admission resource used. Entries will include who they saw, where they saw them, whether it was emergency or routine, the reason for any A&E visit and length of any hospital stay.

Participants will be contacted via telephone by a researcher at 30 and 90 days post randomisation to complete a proforma which captures use of NHS services detailed in patient diaries from discharge. These estimates will be triangulated with electronic NHS records to check for accuracy. Appropriate unit costs will be applied to the NHS resources used by each trial participant. Similarly, the costs of the intervention will be estimated by

ISRCTN: 64639614 IRAS: 313485 CPMS: 53277

calculating the average cost of providing the intervention to patients. EQ-5D -5L QALYs will be estimated using the area under the curve approach and will be adjusted by time. Cost and effectiveness (utility) will be analysed as intention to treat and missing data will be imputed using multiple imputation. In the deterministic analysis, mean values of cost and effectiveness (utility), derived from generalized linear model adjusting for potential confounders, will be used as a representative value for calculating ICER (incremental cost-effectiveness ratio).

Uncertainty around estimates of CE and CU will be explored using cost effectiveness/utility acceptability curves (CEACs), which express uncertainty of outcome as a function of willingness to pay for a unit of outcome.

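### Change from baseline in SGRQ-C and EQ-5D-5L cannot be calculated as written, because neither instrument is scheduled before day 7 after randomisation

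*Protocol*

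**What the plan says.** The analysis text in protocol section 10.3.3 reads: "Mean change in quality of life over 90 days (SGRQ-C, EQ5D5L) from baseline will be calculated".

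The times of measurement are set in three places, and they agree with each other:

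- Section 3.4, secondary outcome 5: "St Georges Respiratory Questionnaire for COPD (SGRQ-C) and EQ-5D-5L days 7, 30 and 90 post-randomisations".
- Section 7.8: the first assessment is at "7 days post-randomisation (within 10 days of the scheduled assessment"), a second follows at day 30, and the last is at "90 days post randomisation (within 14 days of the scheduled assessments): SGRQ-C and EQ-5D-5L".
- Appendix 1: the SGRQ-C and EQ-5D-5L rows each carry three marks, at 7, 30 and 90 days after randomisation, and none at screening or on days 1 to 5.

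Section 7.7 puts the baseline assessment alongside randomisation and lists its content: "Baseline assessment will include sociodemographic details, full medical history, COPD history (confirmation of diagnosis and severity), details of index admission and NIV management". The same section adds only the Borg scale, the sputum scale and the sleep questionnaire for days 1 to 5. Table 2 of baseline variables (section 10.3.1) has no quality-of-life score.

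For the economic evaluation, section 10.9 says that EQ-5D-5L "QALYs will be estimated using the area under the curve approach", without saying where the curve starts.

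**The concern.** A change from baseline needs a value taken before the treatments diverge, and the schedule provides none for either instrument. An analyst who follows section 10.3.3 would have to choose a substitute after the event, in an open-label trial. The obvious choice is day 7, which comes after randomisation and, for most patients, probably after weaning. Subtracting a value that the treatment may already have changed can remove or reverse the effect being estimated. The same gap leaves the EQ-5D-5L curve for QALYs without an observed starting point.

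**Working it through.** **1. Stated analysis against schedule.** Section 10.3.3 needs a baseline SGRQ-C and EQ-5D-5L. Sections 3.4 and 7.8 and Appendix 1 schedule each instrument three times, all after randomisation. Section 7.7 includes neither at baseline. The number of scheduled pre-randomisation measurements is 0.

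Table 1 in section 7.6 appears under a baseline heading and names both instruments. It also lists mortality, readmissions and relapse and gives no times, so it is an inventory of worksheet data and not a baseline visit.

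**2. How far weaning has gone by day 7.** Inputs from section 10.1: at 2.71 days, cumulative weaning is 0.50 (standard) and 0.667 (accelerated), and death is 0.054 in both arms. Assume constant cause-specific hazards.

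- Total hazard per day = −ln(1 − F_wean − F_death) / 2.71. Standard: −ln(0.446)/2.71 = 0.298. Accelerated: −ln(0.279)/2.71 = 0.471.
- Weaning share of the hazard = F_wean / (F_wean + F_death). Standard: 0.50/0.554 = 0.9025. Accelerated: 0.667/0.721 = 0.9251.

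This model reproduces the plan's own sample size:

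- Weaning hazard ratio = (0.9251 × 0.471)/(0.9025 × 0.298) = 1.62.
- Events at two-sided 5% and 80% power = 4 × (1.960 + 0.842)² / (ln 1.62)² = 135.
- 135 / mean(0.9025, 0.9251) = 147.7, and 147.7/0.9 = 164.1, against the stated 164.

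Cumulative weaning at day 7 = share × (1 − exp(−7 × total hazard)):

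- Standard: 0.9025 × (1 − exp(−2.086)) = 0.79.
- Accelerated: 0.9251 × (1 − exp(−3.297)) = 0.89.

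These are extrapolations to 7/2.71 = 2.6 times the planning time. The protocol does not state them. The weaning clock starts at the qualifying blood gas, up to 24 hours before randomisation, so day 7 after randomisation can be day 8 on that clock. The 10-day window allows the first questionnaire as late as day 17.

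**3. What a day-7 baseline would do.** Let the true between-arm difference in utility be a at day 7 and b at day 90. The difference in change is b − a. The values below are illustrative.

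| a (day 7) | b (day 90) | difference in change |
|---|---|---|
| 0.10 | 0.10 | 0.00 |
| 0.10 | 0.05 | −0.05 |
| 0.10 | 0.00 | −0.10 |

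In the first row a sustained benefit disappears. In the other two a benefit that fades appears as harm.

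**4. The QALY gap.** Visits at days 7, 30 and 90 support a trapezoid over 83 of 90 days. The unobserved part is 7/90 = 7.8%, or 17/90 = 18.9% for a participant first assessed 10 days late. If mean utility differed between arms by an assumed 0.05 to 0.20 throughout the gap, the difference left out is d × gap/365.25:

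- 7 days: 0.05 × 7/365.25 = 0.001 to 0.20 × 7/365.25 = 0.004.
- 17 days: 0.002 to 0.009.

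**The case against.** **The existing text already allows a valid comparison.** Section 10.3.3 has a general rule that follow-up measurements are described and continuous variables compared between arms by t-test or Mann-Whitney. SGRQ-C and EQ-5D-5L can therefore be compared at each visit as the text stands. This is right. A reader might infer that the trial has no usable quality-of-life comparison, and the document does not support that. Only the change-from-baseline sentence fails.

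**QALYs can be calculated.** A reader might also infer that the area-under-the-curve analysis is invalid. Section 10.9 names no day-0 anchor, an area over days 7 to 90 can be computed from the schedule, and an area from randomisation needs only a stated starting utility. Such detail is commonly left to an analysis plan, which is not shown here. The 7.8% is a share of time, not a bias in the QALY difference. This stands, so the QALY point is a consequence to settle and not an error in its own right.

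**The arms may differ after day 7 too.** It is tempting to call days 0 to 7 the only period in which the treatments differ. On the extrapolation above, 21% and 11% are not weaned by day 7 (some of them dead), and section 4 allows for later differences in relapse and readmission. That claim is not made here.

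**Other ways to supply a baseline do not work.** Multiple imputation cannot recover a variable scheduled in no participant without an outside assumption. Nor can a statistical analysis plan create the measurement. Reading the 10-day window as also allowing a visit shortly before day 7 still gives no pre-randomisation value.

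**Conclusion.** Section 10.3.3 promises an analysis that the protocol's own schedule cannot supply. That rests on the text alone and needs no assumption.

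The harm from using day 7 instead is conditional. No section says day 7 will serve as baseline, and the 79% and 89% assume a constant hazard. The stated medians of 2.71 and 1.71 days are enough to show that more than half of each arm is expected to be weaned well before day 7.

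The QALY consequence is small in absolute terms, about 0.001 to 0.004 for a 7-day gap under the assumed utility differences. The point affects part of secondary outcome 5 and the anchoring of outcome 8. The primary outcome and the sample size of 164 do not depend on it. It should be fixed before analysis.

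**What to change.** - **Quality of life.** Replace the change-from-baseline sentence in section 10.3.3 with a between-arm comparison of SGRQ-C and EQ-5D-5L at days 7, 30 and 90, adjusted for the minimisation factors in section 7.3. The adjustment is good practice after minimisation and does not itself correct an error. Cost: wording only.
- **Consistency.** Reconcile sections 3.4, 7.6 (Table 1), 7.7, 7.8 and 10.3.3 and Appendix 1, so that no section implies a baseline measurement that is not taken.
- **QALYs.** Either start the area at randomisation with one common assumed utility in both arms, varied in a sensitivity analysis, or state that the area covers days 7 to 90 only. Randomisation justifies a common value. With a straight line from u0 at day 0 to u7 at day 7, the area is 7 × (u0 + u7)/2, so u0 cancels from the difference between arms, apart from early deaths and unequal assessment dates. Cost: one or two sentences.
- **Optional.** Collect EQ-5D-5L before randomisation for patients still to be recruited, and adjust the QALYs for it. This needs a schedule amendment and adds burden for patients who are still on acute NIV, in a time-critical step for which section 7.2 already allots an average of 60 minutes for consent. It cannot help patients already randomised.

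### The Cox model for mortality starts its clock at discharge, so it leaves out in-hospital deaths and does not match the outcome defined from randomisation

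*Protocol*

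**What the plan says.** Section 3.4 lists the outcome as "Mortality in-hospital and 90-days post-randomisation". Section 7.8 sets the assessment to match: "90 days post randomisation: Healthcare resource utilisation costs; Mortality". The schedule of activities in Appendix 1 records mortality during the hospital stay and at day 90 after randomisation.

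The second paragraph of section 10.3.3 introduces three outcomes together, "In-hospital and 90-day mortality, and readmission within 30-days", and then gives the method: "time from discharge to death and time to readmission will be analysed using a Cox proportional hazards regression model", with covariate adjustment. A log-rank test stratified by centre is the sensitivity analysis, and no other time origin is given for it. The paragraph ends with a second method: "we will compare the proportion adjusted for the covariates (In-hospital mortality=NIVO; Readmission=PEARL".

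The first paragraph of section 10.3.3 states that analyses are by intention to treat, with protocol-adherence analyses as secondary.

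**The concern.** The outcome and its survival model start at different times. The outcome counts every death from randomisation to day 90. The model counts only deaths after a live discharge.

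Two things follow. First, deaths during the index admission, when any harm from stopping NIV too early would be expected to show, cannot contribute to the model. Second, being discharged alive happens after randomisation. If the weaning strategy affects who survives to discharge, the groups compared at discharge are no longer the groups that were randomised. A difference between arms, or its absence, could then partly reflect who was left to be compared. Section 1 itself raises the possibility that shorter treatment is less effective and that respiratory failure recurs, so the mortality comparison should not be open to this.

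**Working it through.** **1. Definition against model**

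| | Outcome (3.4, 7.8) | Cox model (10.3.3) |
|---|---|---|
| Time origin | Randomisation | Discharge |
| Patients | All randomised | Discharged alive |
| In-hospital deaths | Counted | Cannot be included |
| End of observation | Day 90 from randomisation | Not stated; mortality is collected to day 90 from randomisation |

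If observation ends at day 90 from randomisation, time at risk after discharge is 90 minus the day of discharge. With assumed discharge on day 10 or day 20 it is 80 or 70 days. The model therefore does not estimate mortality over a common 90-day period.

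**2. The plan's own figures**

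The protocol gives no power calculation for mortality. The relevant inputs are in section 10.1: cumulative incidence of weaning at 2.71 days of 0.50 (standard) and 0.667 (accelerated), cumulative incidence of death of 0.054 in both arms, and a total of 164 including 10% attrition.

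The 164 can be reproduced if constant cause-specific hazards are assumed, which the protocol does not state:

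- Cause-specific hazard of weaning = [−ln(1 − F1 − F2)/t] × F1/(F1 + F2), where F1 is weaning and F2 is death.
- Standard: 0.2689 per day. Accelerated: 0.4358 per day. Ratio: 1.62.
- Schoenfeld's formula (two-sided 5%, power 80%) gives 135 events.
- Eventual probability of weaning: 0.50/0.554 = 0.9025 and 0.667/0.721 = 0.9251, mean 0.914.
- N = 135/0.914 = 147.7, and 147.7/0.9 = 164.1.
- Expected events at 74 per arm: 66.8 and 68.5, against the stated 67 and 69.

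So 164 corresponds to about 148 patients (74 per arm) after attrition.

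**3. Deaths that cannot enter the model**

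- All randomised: 0.054 × 164 = 8.9, about 9.
- After attrition: 0.054 × 148 = 8.0, about 8.

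These are deaths as the competing event, that is, before successful weaning from acute NIV. Patients on home ventilation are excluded, so these are inpatient deaths. The count uses only the 5.4% and needs no hazard assumption. It covers deaths to day 2.71 on the weaning clock, which starts at the qualifying blood gas, up to 24 hours before randomisation.

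Later in-hospital deaths would add to it, but the protocol gives no total for eligible patients. Section 2 quotes 9.2% inpatient mortality at the authors' own service, which would be 0.092 × 164 = 15.1. That figure is not limited to low- and medium-risk patients who have reached weaning. As an assumption only, the range is about 9 to 15.

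**4. What the choice of origin can do (assumed counts, 82 per arm)**

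| Deaths in hospital + later: standard | Accelerated | 90-day risk ratio from randomisation | Risk ratio among those discharged alive |
|---|---|---|---|
| 4 + 8 | 9 + 3 | (12/82)/(12/82) = 1.00 | (3/73)/(8/78) = 0.40 |
| 4 + 8 | 8 + 8 | (16/82)/(12/82) = 1.33 | (8/74)/(8/78) = 1.05 |

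In the first row, equal 90-day mortality looks like a benefit of accelerated weaning. In the second, an excess of deaths nearly disappears. The counts show the mechanism and are not a forecast.

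**The case against.** The strongest reply is that in-hospital deaths are analysed elsewhere, and this is right. Section 10.3.3 also compares the in-hospital mortality proportion adjusted for NIVO. Section 10.3.2 treats death as a competing risk in the primary analysis. Section 9 sends index-admission deaths to the DMC, TSC, sponsor, REC and HRA, and section 10.6 lets the DMC consider a survival analysis. A reader might infer that the plan drops in-hospital deaths altogether. The documents do not support that: the loss is confined to the survival model and its sensitivity test.

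It can also be said that the SAP may settle the clock. But the protocol has not left the origin open. It states one, and that origin conflicts with its own outcome.

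Other stronger readings also fail:

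- **Readmission uses the wrong clock.** It does not. The outcome is "Readmissions 30-days post-discharge", so discharge is its own origin. It needs only a label saying that it is conditional on live discharge.
- **The 30-day readmission limit is contradicted by the economic data.** Section 10.9 says "NHS resource use (primary, secondary and community care) and associated costs will be captured up until 90 days post-randomisation", but this is resource use for costing. A separate 30-day clinical endpoint does not contradict it.
- **About 14 deaths before weaning would be lost.** That figure extends an unstated constant hazard beyond day 2.71 and uses 82 per arm before attrition.
- **Length of stay is analysed wrongly.** The t-test and Mann-Whitney rule is generic and does not name length of stay. Another method would be a preference.
- **Discharge is expected to come earlier with accelerated weaning.** Section 2 mentions a shorter hospital stay only conditionally. The argument needs only that weaning strategy may affect live discharge.

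**Conclusion.** The point stands for mortality. The Cox model in section 10.3.3 cannot analyse in-hospital mortality, and it estimates 90-day mortality only in patients discharged alive. It contradicts sections 3.4 and 7.8 and is not an intention-to-treat comparison. The log-rank sensitivity test names no other origin, so it appears to have the same fault.

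On the plan's own 5.4%, about 9 of 164 patients (about 8 of 148 after attrition) would die by day 2.71 and be absent from the model. The full number is unknown because total in-hospital mortality in eligible patients is not given. The direction of any bias cannot be predicted from the documents; the assumed counts show only that it could be material.

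Mortality is a secondary outcome without its own power calculation. The primary analysis and the sample size of 164 are unaffected, and in-hospital death keeps a separate planned comparison. The wording is nevertheless wrong as it stands and should be corrected before analysis.

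**What to change.** Amend section 10.3.3, and make the SAP agree, as follows:

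1. **90-day mortality:** Cox regression of time from randomisation to death from any cause, in all randomised patients by allocated arm, censored at day 90 or when last known alive if earlier. Run the centre-stratified log-rank sensitivity test on the same clock and population.
2. **In-hospital mortality:** state that it is analysed only as the NIVO-adjusted proportion of all randomised patients, and remove it from the Cox sentence.
3. **30-day readmission:** keep the discharge origin as defined, and label the result as conditional on live discharge.

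The cost is a change of wording. The planned Cox model already needs the date of death, and the time of randomisation is needed to check the 24-hour eligibility limit. Section 7.10 continues mortality collection to day 90 after withdrawal unless the participant objects. No endpoint, visit or sample size changes.
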